4.4 Recruitment

Recruitment for the study will start after FDA approval of the Investigational Device Exemption Application (IDE) and the Institutional Review Board (IRB) approvals at respective study sites.

The parent(s) or legal guardian(s) of the patients who meet the inclusion and exclusion criteria will be clearly informed on the details of the study, including the potential benefits and risks to the patient prior to their enrollment in this study. One or both parents (as appropriate and as required by local IRB) must give their permission unless one parent is deceased, unknown, incompetent or not reasonably available, or when only one parent has legal responsibility for the care and custody of the child per 21 CFR Part 50.55(e). The parent's or legal guardian's consent must be documented via signature and date on the Patient Informed Consent form. Patients will be considered enrolled in the study after the informed consent has been signed and a copy provided to the parents/guardian.

4.5 Patient withdrawal

The parent(s) or legal guardian(s) of the patients are free to withdraw their child from the study at any time without having to justify their decision. When a patient is withdrawn from a study, the parent(s) or legal guardian(s) will be contacted and given the opportunity to provide information about the reason(s) of withdrawal and possible occurrence of an AE.

Patients will be withdrawn from the study at any time for the following reasons:

- Patient no longer requires CRRT and ends therapy prior to receiving at least 20 hours of CRRT treatment,
- Patient requires a non-HF20 filter,
- Interruption of more than 4 hours from CRRT therapy (>4 hr interruption),
- More than one interruption of CRRT on the HF20 set regardless of duration, or

• Investigator Discretion

Reason for withdrawal will be recorded in the electronic Case Report Form (eCRF).

If withdrawal is related to the possible occurrence of AEs, the patient will be followed up according to the AE procedure.

4.6 Analysis Population Definitions

Full Analysis Set (FA): The Full Analysis Set is based on the intent-to-treat principle and includes any patient who received CRRT on the Prismaflex HF 20 Set for any period of time.

Per-Protocol Analysis Set (PP): The Per-Protocol Analysis Set defines a subset of the FA including patients who:

- fulfilled all inclusion criteria
- did not meet any of the exclusion criteria
- received at least 20 hours of CRRT treatment on the HF20 filter with no more than 1 interruption which may have included a filter change
- did not have major protocol deviations that might impact the assessment of the primary endpoint
- have available measurements for the primary endpoint (BUN) at baseline (within 1 hour prior, and 15 min after initiation of CRRT) and at 24 hours (±1 hour) from start of CRRT

5. PATIENT TREATMENT

5.1 Treatment details

All patients will be followed from the time of obtained informed consent through the time they end participation in the study. Patients will be treated for a minimum period of 20 hours of the first 24 hours. They can be treated up to 72 hours on the same Prismaflex HF20 Set. In case of interruption at less than 24 hours, a subject may receive a second HF20 set. BUN, creatinine and bicarbonate are to be measured for statistical analysis at initiation of CRRT and at 12 hour intervals during CRRT treatment. During study CRRT treatment, activated clotting time (ACT), partial thromboplastin time (PTT), and activated partial thromboplastin time (APTT) (applicable to heparin use only) will be

measured as determined by the standard of care at each site. Patient ionized calcium and extracorporeal circuit (post circuit) ionized calcium will be measured per local standard of care (applicable to citrate use only). Each patient may be treated on the same Prismaflex HF 20 Set for up to 72 hours.

Treatments will be performed according to this clinical protocol and in accordance with the Instructions for Use (IFU) for the Gambro Prismaflex HF20 Set and the Operators Manual for the Prismaflex System Software Version 7.10 or 7.20. Treatments will be performed in accordance with the IFU and Operations Manual and managed in accordance with the local standard of care for pediatric CRRT.

5.2 Procedure to Minimize Fluid Balance Errors

All CRRT study clinicians will be trained on the use of Prismaflex System Software Version 7.10 and 7.20 and will have previously used Prismaflex in clinical practice. The training will also cover specific features in the Prismaflex System Software Version 7.10 and 7.20 that support safe and effective use of the Prismaflex HF20 Set, including:

- Prismaflex System Software Version 7.10 and 7.20 on-screen support for blood priming the Prismaflex HF20 Set
- Setting Prismaflex System Software Version 7.10 and 7.20 UF error limits during treatment setup
- Best practice during Prismaflex System Software Version 7.10 and 7.20 fluid bag changes and in handling of Prismaflex System Software Version 7.10 and 7.20 UF alarms

Monitoring for fluid balance errors will be based both on the UF alarms in Prismaflex System Software System Version 7.10 and 7.20 as well as through monitoring of the Prismaflex System Software Version 7.10 and 7.20. Measurement of fluid bag weights will employ an external scale. It is up to the discretion of the responsible physician investigator to decide how these will be measured. If performed, local clinical procedures are to be followed.

5.3 Prismaflex System Software Version 7.10 and 7.20 Alarm System for UF Errors

Prismaflex System Software Version 7.10 and 7.20 alarms will be issued based on immediate deviations between delivered and expected fluid weight on each bag of >20 g. A treatment shutdown will be issued and alarm given based on the cumulative UF error in a 3 hour sliding window.

The determination of an acceptable Prismaflex System Software Version 7.10 and 7.20 UF error limit follows from the UF rate error, which is not to exceed 0.1 mL/kg/min in order to avoid complications, up to and including hemodynamic instability. The UF error limit default is determined based on the cumulative UF rate error over a sliding 3 hours window. The Patient Fluid Removal accuracy (PFR acc) of the Prismaflex System Software Version 7.10 and 7.20 is considered in this interval (± 70 mL per 3 hours):

UF default error limit = $0.1 \text{ mL/kg/min} \times 180 \text{ min} \times BW - PFR$ acc

This default UF error limit is calculated based on the patient weight entered during the set-up phase of the treatment. As an example, a patient weight of 10 kg would result in a default error limit of:

UF default error limit = $0.1 \text{ mL/kg/min} \times 180 \text{ min} \times 10 \text{ kg} - 70 \text{ mL} = 110 \text{ mL}$

Determination of the actual limit may follow the calculated default value, but is ultimately up to the discretion of the prescribing physician investigator. In consideration of the patient's condition, a more stringent limit may apply.

The prescribed limit is settable down to a limit of 60 mL/3 hours and is entered by the device operator. This is a mandatory action in order to be able to proceed to patient connection. Once set, the UF error limit is active throughout the treatment.

Should the preset UF error limit be reached during treatment, the device monitoring system will issue an alarm and terminate the treatment. Treatment at this point cannot be re-started on the same filter. Occurrence of such events shall prompt a call to the investigator and should alert the personnel to reassess the patient before continuation of the treatment on a new disposable set.

5.4 Fluid Overload Calculations

Fluid overload will be calculated by the methods used by Goldstein and the Prospective Pediatric CRRT Registry Group: [Fluid in (L) – Fluid out (L)] /ICU admission weight (kg) * 100. The initial fluid overload will be calculated at the time of Study CRRT initiation and then at 12 hour intervals from that point until the end of the study. Blood pressure data, including mean arterial pressure, will be recorded either non-invasively or via an indwelling arterial catheter (present as part of clinical care and not for study purposes alone) at Study CRRT initiation and at 1 hour intervals from that point until end of study. If CRRT is discontinued before a 6 hours time point for hemodynamic reasons or before a 12 hour time point for reasons related to fluid balance, the last measurements available prior to CRRT termination will be recorded as end of treatment.

5.5 Prismaflex Fluid Balance Data

There are two ways to track fluid balance data from the Prismaflex System. The first consists of recording data from the History Display section of Prismaflex and the second one is from the review of the log files on the Prismaflex technical data card.

5.5.1 Log Files on Technical Data Card

Prismaflex System Software Version 7.10 and 7.20 automatically saves a log file at the end of each CRRT treatment. These log files track all events and alarms occurring during Prismaflex CRRT to include pressures, scale weights, pump speed data, etc.

Logging data are saved on the Prismaflex technical data card after a completed treatment, during the unload sequence of the disposable set. The data contained in these files mirror the information that was displayed on the GUI of the Prismaflex during treatment, such as prescription data, treatment events (alarms, bag changes), as well as treatment data including UF volumes.

Data from the Prismaflex technical data card will be used for the following:

- to allow for the investigation of reported study related events
- as a source of data to allow for the analysis of technical parameters, including alarm rates, stability of software, etc.

5.6 Treatment: Prescriptive Guidelines

The treatment parameters (eg, flow rates, time, etc.), dialysates, replacement fluids and anticoagulants will be at the discretion of the physician investigator, but will be recorded on the eCRFs and must be consistent with the labeling as follows:

- Minimum combined convective/diffusive prescribed small solute clearance: 2000 mL/h./1.73m² patient BSA
- Maximum Blood Flow Rate: 100 mL/min
- Maximum TMP: 450 mmHg/kPa

5.6.1 Dialysates

Only prescribed commercially available sterile dialysate solutions with a density similar to saline solutions will be used with the Prismaflex System Software Version 7.10 and 7.20. Sterile dialysate solutions should be standardized and formulated in accordance to the patient's clinical needs. The use of nonsterile dialysates could induce risks of bacterial or pyrogenic contamination for the patient.

5.6.2 Replacement Fluids

Only prescribed commercially available replacement solutions with a density similar to saline solutions and which are labeled for intravenous injections will be used. Replacement Fluids should be standardized and formulated in accordance to the patient's clinical needs.

5.6.3 Anticoagulants

Anticoagulation plays an important part in extending filter life by retarding plugging and clotting. The type of anticoagulants used will be as prescribed by the physician. The IFU for the Prismaflex HF20 Set provides the following recommendations for heparinization below in Section 5.6.3.1 Anticoagulation Considerations.

5.6.3.1 Anticoagulation Considerations

According to the literature, continuous heparinization at a rate of 10 to 20 IU/kg/h ensures proper operation of the extracorporeal circuit when performing treatment with patients having normal coagulation status. Depending on the patient's condition, however, heparinization can be lowered to < 5 IU/kg/h. Heparinization can be controlled by partial thromboplastin time (PTT) measurements: in this case, PTT could be maintained at 20 to 30 seconds over baseline.¹⁸ Many centers check Activated Clotting Times (ACTs) instead of PTT. Each center will follow its own clinical practice for circuit heparinization.

Many US centers, including those involved in this application, use regional citrate anticoagulation to prevent clotting of CRRT circuits. The ppCRRT Registry Group has shown that such practices lead to comparable filter lifespan with fewer side effects¹ and regional citrate anticoagulation has been suggested as the preferred method in the recent KDIGO AKI guidelines.¹⁹ As general guidelines, some sites have altered their regional citrate protocol from this original published protocol, but all centers will perform their citrate protocol to achieve the following goals per their standard of care:

- Acid-citrate-dextrose [ACD (Baxter, McGaw Park)] will be the standard citrate solution and will be infused either via an external dedicated pump or the Prismaflex[®] Pre-Blood Pump (PBP) at a rate that is per local standard of care.
- A calcium containing solution will be infused at the patient's return access or via a separate central line in composition, concentration and at a rate that is per local standard of care.
- Initial citrate rates will be decreased by 50% of standard for patients with expected immature/decreased hepatic metabolic function (patients <1 year of age, or with acute/chronic hepatic failure).
- Paired (post filter) circuit and patient ionized calcium levels will be obtained per local standard of care.
- In addition, paired ionized calcium levels will be drawn one hour after any change in citrate or calcium infusion rates.
- The goals of regional citrate anticoagulation will be to achieve a circuit ionized Ca level of 0.25 to 0.45 mmol/L and a patient ionized Ca level of 1.0-1.5 mmol/L.
- Twice daily patient total calcium levels will be drawn to assess for total hypercalcemia or citrate accumulation.
- Patients with total calcium levels >12.5 mg/dl (hypercalcemia) but with desired ionized Ca levels will have the CaCl₂ rate decreased per local standard of care.
- Patients with total calcium levels >12.5 mg/dl AND low ionized Ca levels
 < 0.9 mmol/L will be diagnosed with citrate accumulation. The treatment for citrate accumulation will be managed by local standard of care but will include decreasing the citrate infusion rate or discontinuing it, increasing citrate clearance by increasing dialysis and/or replacement fluid rates, or both. Hourly paired ionized Ca levels will be obtained until the patient ionized calcium is > 1.0 mmol/L.

This protocol, or slight variations to it, has been reported in numerous pediatric publications.^{2,20-22} Given the recent calcium chloride supply shortage in the US, a standard conversion will be used to substitute calcium gluconate to provide equimolar amounts of calcium to the patient. All of the study sites have over 6 years of experience with this citrate anticoagulation protocol.

5.6.4 Hypothermia prevention

When treating infants and children with the Prismaflex HF20 Set, the volume of the extracorporeal circuit and the high exchange volume/patient weight ratio may cause hypothermia. It is recommended to warm the blood with the Gambro Prismaflow Blood and Fluid Warmer or any other standard warming devices used in treatment of patients with a weight ≥ 8 kg and ≤ 20 kg.

5.6.5 Priming the Extracorporeal Circuit

Circuits will be primed per local standard of care. Since the extracorporeal volume (ECV) of the circuit is < 10% of the blood of patients in this study (weight 8-20 kg), priming with blood products will not be mandated, but the site may choose to do so based on their local standard of care and patient stability.

5.7 Contact and Delivery of Study Material:

Investigators that will be participating in this study will be sent a copy of this protocol along with any applicable regulatory documents. Once this protocol and regulatory documents have been received by a given study site, the study site will be contacted by sponsor's Clinical Study Monitor to encourage the site to complete and return the forms in an expeditious manner.

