3.3 Study product and material

The Prismaflex HF20 Set is indicated for use only with the Prismaflex System equipped with software Version 7.10 and Prismaflex System Software Version 7.20 in providing

continuous fluid management and RRT. The system is intended for patients who have AKI, fluid overload or both, taking into consideration the patient's access, blood flow, body weight and the extracorporeal blood volume. The Prismaflex HF20 Set is intended for use in the following veno-venous therapies: CVVH, CVVHD and CVVHDF. The Prismaflex HF20 Set should be restricted to patients with a body weight $\geq 8 \text{ kg}$ (17.6 lb.) and <20 kg (44.09 lb).

The Prismaflex HF20 Set incorporates a membrane which is identical to the membrane used in the Gambro HF1000 and HF1400 sets, both of which have been previously cleared by the FDA for marketing and clinical use in the United States (K042938). The Prismaflex HF20 Set dialyzer contains the Polyamix[™] membrane, which is hemocompatible and able to effectively reject dialysate contaminants. More specifically, the membrane contains 0.22 m² of polyarylethersulfone/polyvinyl-pyrrolidone membrane, which is almost identical in composition to the membrane used in other Gambro Polyflux hemodialyzers (ie, Polyflux 6H, 140H, 170H, 210H) which have been previously cleared by the FDA for marketing and clinical use in the US. Therefore, low treatment-induced inflammation is to be expected from the use of the Prismaflex HF20 Set which utilizes a similar membrane as that studied by Schindler et. al.⁹ The membrane in the Prismaflex HF20 Set has an inner diameter of 215 µm and a wall thickness of 50 µm and is sterilized by steam, which is the same sterilization method used for the previously cleared Gambro Polyflux hemodialyzers. The blood priming volume of the extracorporeal circuit for the HF20 set is 60 mL and is lower than previously cleared Gambro Polyflux hemodialyzers and CRRT circuits due to its pediatric application.

Gambro will provide each investigational site with one Prismaflex System equipped with software version 7.10 or Prismaflex System Software Version 7.20. The provided machine may only be used on patients participating in the clinical study according to the FDA IDE regulations.

The FDA has not given 510(k) clearance for use of either the Prismaflex HF20 Set or the Prismaflex System Software Version 7.10 and Prismaflex System Software Version 7.20 for use in patients weighing <20 kg (44.09 lbs).

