4.2 Inclusion criteria

A subject must meet ALL of the following inclusion criteria in order to participate in this study:

- 1. Patients with a hospital admission body weight ≥ 8 and ≤ 20 kg (ie, ≥ 17.6 and ≤ 44.09 lbs).
- Patients with AKI defined as either 1) AKI by the Kidney Disease Improving Global Outcomes (KDIGO) Acute Kidney Injury Guideline serum creatinine criteria, which is a ≥50% rise in serum creatinine over baseline or a 0.3 mg/dL SCr rise in 48 hours OR 2) as AKI by the Pediatric modified Risk, Injury, Failure, Loss, End-Stage Renal Disease (pRIFLE) criteria which is a 25% reduction in estimated creatinine clearance,¹⁶ OR 3) a serum creatinine ≥1.2 mg/dL.

OR

Patients with severe fluid overload, defined as a >10% fluid accumulation relative to the ICU admission.

- 3. Patients who have received RRT previously can be included in the study if >24 hours have elapsed since their previous RRT treatment.
- 4. Provide written informed consent from one or both parents, as required by the local IRB or legal guardians, unless one parent is deceased, unknown, incompetent or not reasonably available, or when only one parent has legal responsibility for the care and custody of the child per 21 CFR Part 50.55(e).

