4.3 Exclusion criteria

Exclusion criteria are the following:

1. The following hemoglobin exclusion criteria apply:

| Weight | Starting Hgb (g/dl) | Exclusion Criteria |
|-------------|---------------------|--------------------|
| 8.0-20.0 kg | <7.0 | Excluded |

| 8.0-12.0 kg | <8.0 | Excluded unless blood prime is used |
|--------------|------|-------------------------------------|
| 12.1-20.0 kg | <7.5 | Excluded unless blood prime is used |

2. Children who are wards of the state.

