5.8 Data to be Collected

5.8.1 Patient Information to Be Collected Prior to Initiation of Treatment

The following data will be collected and recorded on the Case Report Forms for Screening.

- 1. Coded Patient I.D.
- 2. Inclusion/Exclusion Criteria
- 3. Signed Patient Informed Consent
- 4. Patient Demographics
 - a. Gender
 - b. Date of Birth
 - c. Hospital Admission Weight, Height, and Body Surface Area
 - d. Calculated Intravascular Blood Volume
- 5. Patient Medical Information
 - a. Cause of Acute Kidney Injury

- b. Diagnosis
- c. Vital Signs
- d. Medication History for the Last 7 Days
- e. Medical and Surgical History

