### 8. DEMOGRAPHICS AND BASELINE CHARACTERISTICS

Demographic and baseline characteristics will be summarized using descriptive statistics for all subjects as well as for each clearance specification subgroups (if applicable).

Demographic data include age, gender, race, ethnicity, height, weight at hospital admission, body surface area and calculated intravascular blood volume. Calculated intravascular blood volume will be calculated as 70 ml multiplied by the patient's hospital admission weight in kilograms.

Baseline characteristics collected on the eCRF also include medical history and acute kidney injury history. Acute kidney injury (AKI) history recorded data will include: cause of AKI, current ICU diagnosis, prior CRRT treatment, and end date and time of last CRRT treatment.

Lab data including: serum sodium, potassium, chloride, bicarbonate, serum creatinine, phosphorus, total calcium, albumin, beta 2 microglobulin, BUN, and FUN are collected at baseline as well as at screening and every 12 hours for up to 72 hours after CRRT initiation. Vital sign data including: temperature, systolic/diastolic blood pressure, mean arterial pressure, pulse, and respiratory rate are captured at baseline as well as screening and hourly up to 72 hours after CRRT initiation. Mechanically ventilated patients will also be recorded every 12 hours after initiation of CRRT.

The following describes the summary of various types of demographic and baseline data either as continuous data, frequency tabulations or as listings:

- 1. Age, height, hospital admission weight, body surface area, and calculated intravascular blood volume will be summarized as a continuous variable.
- 2. The frequencies for gender, race and ethnicity will be tabulated.
- 3. Medical conditions and surgery items recorded in the medical history eCRF will be coded to a Medical Dictionary for Regulatory Activities (MedDRA, Version 16.1 or higher) and listed by system organ class and preferred term
- 4. AKI history will be listed for each patient.
- 5. All laboratory samples collected at baseline will be summarized as continuous variables for both analysis populations.

6. All vital sign values collected at baseline will be summarized as continuous variables populations except for the number of patients mechanically ventilated at baseline which will be presented as a frequency and percentage.

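### Does the protocol's reason for not mandating blood priming fail for the lightest eligible children?

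*Protocol*

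**What the plan says.** Protocol 5.6.5 opens by leaving circuit priming to each site's usual practice. It then gives a reason for imposing no blood prime: "Since the extracorporeal volume (ECV) of the circuit is < 10% of the blood of patients in this study (weight 8-20 kg", and concludes that "priming with blood products will not be mandated". It ends by returning the choice to the centre: "the site may choose to do so based on their local standard of care and patient stability".

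Three other places bear on the figure:

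- Protocol 3.3 gives the circuit volume: "The blood priming volume of the extracorporeal circuit for the HF20 set is 60 mL".
- Protocol 5.8.1 lists "Calculated Intravascular Blood Volume" among the screening data, with no formula.
- SAP section 8 supplies a formula: "Calculated intravascular blood volume will be calculated as 70 ml multiplied by the" hospital admission weight in kilograms. The result is summarized with the demographic data.

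Eligibility in Protocol 4.2 uses the same weight ("Patients with a hospital admission body weight") and starts at 8 kg inclusive. Separately, the hemoglobin table in Protocol 4.3 marks some children in the 8.0-12.0 kg and 12.1-20.0 kg bands as "Excluded unless blood prime is used".

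**The concern.** The sentence in Protocol 5.6.5 covers the whole 8-20 kg range, uses a strict inequality, and is offered as the reason for a decision about treatment. A reader who takes the circuit volume from the protocol and the blood-volume formula from the SAP finds that it fails at the bottom of the range. That is where the circuit takes the largest share of a child's blood.

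If the priming instruction rested on that inequality, a group of eligible children would be treated under a rationale that did not apply to them. If the protocol instead assumed a larger blood volume, the two documents would be using different values for the same quantity.

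**Working it through.** **Inputs**

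- Circuit volume: 60 mL (Protocol 3.3).
- Blood volume: 70 mL per kg of hospital admission weight (SAP section 8).
- Lowest eligible weight: 8 kg (Protocol 4.2).
- Stated share: below 10% over 8-20 kg (Protocol 5.6.5).

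**Formula.** Share = 60 / (70 × weight).

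| Weight (kg) | Blood volume (mL) | Share |
|---|---|---|
| 8.0 | 560 | 10.71% |
| 8.5 | 595 | 10.08% |
| 9.0 | 630 | 9.52% |
| 10 | 700 | 8.57% |
| 20 | 1,400 | 4.29% |

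**Crossing point.** The share equals 10% at 60 / (0.10 × 70) = 8.571 kg. The stated figure therefore reproduces above about 8.57 kg and does not reproduce from 8.0 to 8.57 kg. That band is 0.571 / 12 = 4.8% of the width of the weight range. The documents give no weight distribution, so this cannot be turned into a number of children.

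**Largest gap.** At 8.0 kg, 10% of 560 mL is 56 mL. The excess is 60 − 56 = 4 mL, or 10.71 − 10 = 0.71 percentage points.

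**Sensitivity to the constant.** Protocol 5.6.5 states no mL/kg, so the value behind it is unknown. At 8.0 kg the break-even is 60 / (0.10 × 8) = 75 mL/kg. Alternatives at 8.0 kg, where 75 and 80 are assumptions:

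- 70 mL/kg: 60/560 = 10.7%
- 75 mL/kg: 60/600 = 10.0%, still not below 10%
- 80 mL/kg: 60/640 = 9.4%

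Above 75 mL/kg the sentence is true for every eligible weight.

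**Where the ratio is used.** The SAP defines no variable, subgroup, population or test from circuit volume over blood volume, and neither of its lists of tables, figures and listings includes it. The sample size (SAP 5.2) and the primary analysis (SAP 12.1) rest on the 24-hour BUN reduction alone. The 70 mL/kg enters only one descriptive baseline summary. Replacing it with another constant k would multiply every child's value by k/70. That adds no information, because admission weight is itself summarized.

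**Whether the instruction depends on it.** If the 10% clause is struck from Protocol 5.6.5, two statements remain: priming follows local practice, and a blood prime is optional at the site's judgment. The instruction to sites is unchanged. The clause is not worded as a per-child check, and the hemoglobin rule in Protocol 4.3 operates without reference to it.

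**The case for a change.** The best case for acting is that the sentence names 8-20 kg without qualification, so one eligible weight at which it fails is enough to make it disagree with the other figures. It is also the only reason the section gives for not requiring a blood prime. Appealing to a larger unstated blood volume does not remove the difficulty, because the protocol and the SAP would then differ on that quantity. Site discretion and the hemoglobin rule do not make the percentage correct, and the repair would cost one sentence or one constant.

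Most of this stands. The arithmetic is right, and the three places do not agree for children of 8.0 to about 8.57 kg.

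Two parts are weaker. First, this is not shown to be an arithmetic error within the protocol. The failing value needs a constant from another document, where it serves a demographic summary and is not tied to priming. Second, a low cost does not justify a change that has no effect. Under either repair, sites would prime as they do now and the results would be read in the same way. What a site did will also be visible: SAP 5.6 records use of a blood prime, and SAP 13.6 lists prescription values by patient.

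**Conclusion.** The mismatch is real but small, and it calls for no change to the plan. With a 60 mL circuit and 70 mL/kg, the share is 10.7% at 8.0 kg and is below 10% only above about 8.57 kg. The excess is never more than 4 mL or 0.71 percentage points. This rests on applying the SAP's descriptive constant to a protocol sentence that states none. Any value above 75 mL/kg makes the sentence hold throughout, and the documents do not show which value its authors used.

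The figure is background reasoning in a paragraph that already leaves priming to local practice, and no endpoint, population, sample size or planned output depends on it. Which blood volume is right, and how circuits should be primed, are not statistical questions, and no view is taken on them here. Reconciling Protocol 3.3, Protocol 5.6.5 and SAP section 8 is housekeeping for the sponsor, with no gain for the trial's conduct or conclusions.
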